#### Background:

In the United States, more than 1 in 5 pregnant women undergo induction of labor. (1) The likelihood of vaginal delivery after induction of labor is increased if the cervix is favorable (Bishop score > 8). (3) However, in women with an unfavorable cervix (Bishop score < 6), cervical ripening is beneficial. (1, 3) Cervical ripening balloon placement is a safe and effective method of cervical ripening in which a Foley catheter is passed through the internal cervical os into the extra-amniotic space and inflated with saline. The balloon then rests against the internal os, physically causing gradual cervical dilation as well as causing the release of prostaglandins from the adjacent membranes and cervix. (3) Compared with prostaglandins, Foley catheter placement has the advantages of being low cost, with reduced risk of uterine tachysystole or fetal heart rate changes. (1)

Several studies have assessed variations in transcervical Foley catheter use. For example, studies have been conducted to assess the potential benefit of increased volume of inflation of the balloon (2), traction on the Foley balloon (4), extra-amniotic saline infusion (3), and the addition of adjunctive agents such as prostaglandins (3) or Oxytocin (4). The use of adjunctive agents is attractive to decrease the interval from induction to delivery, which has the potential to decrease healthcare related costs and improve patient satisfaction.

In a randomized study, Pettker et al found no significant difference in the proportion of deliveries achieved within 24 hours, the induction to delivery interval, or duration of cervical ripening when comparing transcervical Foley catheter alone and transcervical Foley catheter with Pitocin. However, a subgroup analysis of multiparous patients demonstrated an increase in deliveries within 24 hours (91 vs 68%, RR 1.33, 95% CI 1.06-1.67) and an average induction to delivery interval that was 4.6 hours shorter ( $p = 0.046$ ). (4) Though a benefit was suggested in this subgroup analysis, there has been no primary outcome data on multiparous patients undergoing an induction of labor with transcervical Foley catheter and simultaneous oxytocin and the optimal ripening regimen remains unclear.

**Objective:** The purpose of this study is to determine the optimal method for induction of labor in multiparous women with an unfavorable cervix.

**Hypothesis:** Our hypothesis is that using Oxytocin while the cervical ripening balloon is in place will result in more rapid labor courses, without increase morbidity or increasing the need for operative delivery.

Objective: The purpose of this study is to determine the optimal method for induction of labor in multiparous women with an unfavorable cervix.

Hypothesis: Our hypothesis is that using Oxytocin while the cervical ripening balloon is in place will result in more rapid labor courses, without increase morbidity or increasing the need for operative delivery.

Inclusion Criteria:

- Age > 18 years
- Gestational age > 34 weeks
- Prior spontaneous vaginal delivery
- Clinical or ultrasound estimated fetal weight < 4500 grams
- Singleton gestation
- Cervical dilation < 2 cm on admission

Exclusion Criteria:

- Placental abruption, chorioamnionitis, or systemic infection prior to induction
- Rupture of membranes prior to induction
- More than 1 prior cesarean delivery
- Placenta within 2 cm of cervical os
- Any contraindication to vaginal delivery
- Any contraindication to cervical ripening balloon placement or oxytocin administration

Study Protocol:

- Identify patients who are multiparous, who will be undergoing induction of labor, and obtain informed consent either during prenatal care or on admission to labor and delivery.
- Randomize patients to receive cervical ripening balloon (CRB) alone followed by oxytocin or CRB and simultaneous oxytocin for induction via random number generator in sequential opaque envelopes.
- CRB is placed digitally or with a speculum and balloon is inflated with 35 mL of normal saline. Care of the CRB per current MacDonald guidelines. Oxytocin is administered either when the balloon is removed (after 12 hours) or if spontaneously expelled sooner if in the control group, or is initiated when the balloon is placed in the experimental group.
- Fetal monitor and labor management is per current guidelines for all participants.

Statistical Analysis Plan:

Power Calculation: Using the data from Pettker, in the subgroup analysis of multiparous women, the rates of vaginal delivery within 24 hours were 75% and 55% respectively for women receiving transcervical Foley with oxytocin compared with transcervical Foley alone. Under assumption of 80% power and an alpha of 0.05, we estimated we would need 90 patients in each arm to demonstrate a 20% reduction (from 75% to 55%) in primary outcome in the treatment group.

Data Collection: Demographic variables (maternal age, race, parity, gestational age at delivery, indication for induction), time to expulsion of CRB, cervical dilation after expulsion, time to delivery, cesarean delivery rate, operative vaginal delivery rate, perinatal complications (including postpartum hemorrhage, chorioamnionitis, or cervical laceration), neonatal outcomes (including APGAR scores)

Analysis Plan: Intention to treat analysis, calculation of RR, 95% CI. Categorical and continuous variables will be assessed using parametric and non-parametric tests where appropriate.

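### Does the no-increase clause of the hypothesis need its own criterion when 90 per arm is sized only on vaginal delivery within 24 hours?

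*Combined protocol and SAP*

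**What the plan says.** The Hypothesis paragraph, which appears twice, has two parts: faster labor, and this result "without increase morbidity or increasing the need for operative delivery".

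Under Statistical Analysis Plan, the Power Calculation deals with one outcome. It takes from an earlier trial's multiparous subgroup that "the rates of vaginal delivery within 24 hours were 75% and 55% respectively" for Foley with oxytocin and Foley alone, and concludes: "we estimated we would need 90 patients in each arm". The conditions are given as "Under assumption of 80% power and an alpha of 0.05".

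The outcomes behind the second clause are listed under Data Collection: "cesarean delivery rate, operative vaginal delivery rate, perinatal complications", followed by examples of complications and by neonatal outcomes. No expected rates are given.

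The Analysis Plan reads "Intention to treat analysis, calculation of RR, 95% CI", and then: "Categorical and continuous variables will be assessed using parametric and non-parametric tests where appropriate". It states no non-inferiority margin, acceptable upper limit or decision rule for the second clause.

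**The concern.** A claim that something does not increase differs in kind from a claim that something improves. A test of difference that misses significance may reflect equal rates, or a harmful difference the trial was too small to detect. Supporting the clause takes a confidence interval whose upper limit lies below an increase that matters, and the plan does not say what that increase is.

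The risk is in the reporting. Suppose operative deliveries were 18/90 with simultaneous oxytocin and 9/90 without. The test gives p = 0.06, so an author who looked only at p-values could call the clause met although the observed rate had doubled. The outcomes involved (cesarean, hemorrhage, infection) matter to anyone choosing between the two methods, and the stated objective of finding the optimal method depends on them.

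**Working it through.** **1. The plan's own figure.** Inputs from the Power Calculation: p1 = 0.75, p2 = 0.55, power 80%, alpha 0.05 (two-sided assumed, since the plan does not say). Mean rate = 0.65, difference d = 0.20.

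n per arm = [1.960 × √(2 × 0.65 × 0.35) + 0.842 × √(0.75 × 0.25 + 0.55 × 0.45)]² / 0.20²
= [1.960 × 0.6745 + 0.842 × 0.6595]² / 0.04 = 88.09, so 89.

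The stated 90 agrees, and gives 80.8% power. It is the size for the 24-hour outcome only.

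**2. The example.** 18/90 against 9/90:

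- Relative risk = 0.20 / 0.10 = 2.0. SE of log RR = √(1/18 − 1/90 + 1/9 − 1/90) = 0.380. 95% CI = exp(0.693 ± 1.96 × 0.380) = 0.95 to 4.21.
- Risk difference = 10.0 points. SE = √(0.2 × 0.8/90 + 0.1 × 0.9/90) = 0.0527. 95% CI −0.3 to 20.3 points.
- Pooled z-test p = 0.060; Fisher p = 0.094.

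**3. Precision at 90 per arm.** The documents give no event rates, so those below are assumptions. If both arms show the same rate p:

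- Risk-difference half-width = 1.96 × √(2p(1 − p)/90)
- RR limits = exp(±1.96 × √(2(1 − p)/(90p)))

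| Rate in each arm | Half-width, points | RR limits |
|---|---|---|
| 5% | 6.4 | 0.28 to 3.57 |
| 10% | 8.8 | 0.42 to 2.40 |
| 15% | 10.4 | 0.50 to 2.00 |
| 20% | 11.7 | 0.56 to 1.79 |

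**4. Chance that the upper 95% limit rules out a given increase.** Exact binomial enumeration, 90 per arm, true rates equal; log-RR interval (0.5 added if an arm has no events) and Wald interval for the risk difference:

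| True rate | Excludes RR of 2 | Excludes +10 points | Excludes +5 points |
|---|---|---|---|
| 5% | 16% | 86% | 36% |
| 10% | 35% | 61% | 21% |
| 20% | 63% | 40% | 14% |
| 30% | 85% | 32% | 11% |

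With the Newcombe interval, the +10-point column becomes 79%, 58%, 39% and 32%. Power of the test to detect a true doubling is 24% from 5%, 47% from 10% and 84% from 20%. A doubling, 10 points and 5 points are illustrations, not margins taken from the plan.

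The answer turns on the rate and the scale. Relative precision improves as the rate rises, while absolute precision worsens. A 10-point increase is more likely than not to be excluded at 5% and 10%, but not at 20% or 30%. A 5-point increase is unlikely to be excluded at any rate tried.

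**5. What following the plan would produce.** The Analysis Plan calls for a relative risk and 95% CI. Applied to the example, that prints 2.0 (0.95 to 4.21), and the reader sees that a fourfold increase is not excluded.

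**6. Overlap with the sized outcome.** A cesarean is not a vaginal delivery within 24 hours, so it counts as a failure there. At the planning rates, failures are 100 − 75 = 25% with simultaneous oxytocin and 100 − 55 = 45% without, and the cesarean rate in each arm cannot exceed those figures. Extra cesareans in the oxytocin arm would reduce the measured benefit.

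**The case for a change.** The best argument for a change is that the clause is half of the stated hypothesis and is not labelled secondary. The plan offers tests of difference alongside intervals without saying which decides, and settling this beforehand would cost a sentence or two and no patients. The safeguard in step 6 is also partial: faster vaginal births could outweigh extra cesareans, and operative vaginal delivery and maternal morbidity do not enter the sized outcome at all.

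The facts in that argument stand. There is no criterion, the documents leave open whether operative delivery means cesarean, operative vaginal delivery or both, and a non-significant test would not show absence of an increase. The argument falls short on consequence. It guards against a misreading that the plan nowhere proposes, and the planned interval exposes that misreading when it happens. A cautionary sentence with a risk difference would not say what result supports the clause either. That would take a margin, and the documents contain neither a margin nor the event rates from which to judge one.

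**Conclusion.** No change to the plan follows. The clause has no stated criterion, but this is a gap in interpretive detail that analysts fill sensibly from output already planned: relative risks with 95% limits, by intention to treat, on outcomes already being collected. Sizing a trial on its main efficacy outcome alone is ordinary practice. The 90 per arm does what it was calculated to do (89 needed, 80.8% power), and no stated power for the safety outcomes is missed because none is claimed.

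Whether 90 per arm is precise enough for the clause cannot be decided from the documents. Across assumed rates of 5% to 30%, the chance of excluding a doubling runs from 16% to 85%, and of excluding a 10-point increase from 86% down to 32%. These figures rest wholly on assumed rates and illustrative increases, with equal true rates in the two arms. They are a reason to report the upper confidence limit instead of relying on a p-value when the clause is discussed; they do not show a defect in design or analysis.

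### Is a 20-point target, taken from one earlier study's subgroup and worded backwards, too weak a basis for 90 women per arm?

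*Combined protocol and SAP*

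**What the plan says.** The Power Calculation paragraph of the Statistical Analysis Plan relies on a multiparous subgroup of one earlier randomized study: "in the subgroup analysis of multiparous women, the rates of vaginal delivery within 24 hours were 75% and 55% respectively", the first rate for Foley with oxytocin and the second for Foley alone. "Under assumption of 80% power and an alpha of 0.05", it arrives at 90 women per arm. It then describes the aim as "to demonstrate a 20% reduction (from 75% to 55%) in primary outcome in the treatment group". It gives no numbers of women, no interval for 75% against 55%, and no power at any other difference.

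Background describes the same earlier study with a different pair of rates, for deliveries and not specifically vaginal deliveries: "subgroup analysis of multiparous patients demonstrated an increase in deliveries within 24 hours (91 vs 68%, RR 1.33, 95% CI 1.06-1.67". It also reports that the study as a whole "found no significant difference in the proportion of deliveries achieved within 24 hours", and it is candid about how far the subgroup result goes: "Though a benefit was suggested in this subgroup analysis, there has been no primary outcome data on multiparous patients".

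The Analysis Plan paragraph specifies intention to treat, with risk ratios and 95% confidence intervals.

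**The concern.** Three features of the target invite challenge.

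- **Imprecision.** It is a bare point estimate from a subgroup. The only interval in the document belongs to another endpoint (91% against 68%), so a reader could carry that reassurance over to 75% against 55%, where it may not apply.
- **Optimism.** A favorable subgroup result inside an overall null study tends to overstate the effect. The plan uses all of it, and 90 per arm exceeds the computed requirement by one woman per arm. Nothing says that 20 points is the smallest difference that matters.
- **Direction.** One sentence gives 75% to Foley with oxytocin. The next has the treatment group falling from 75% to 55%, against the trial's own hypothesis of faster labor.

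If the true benefit is well below 20 points, the trial would more likely than not end non-significant, and a real gain could be read as none. If the direction mattered to the calculation, the sample size could be wrong as well.

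**Working it through.** **1. The plan's own figure.** Inputs from the Power Calculation: 75%, 55%, 80% power, alpha 0.05. Sidedness is not stated, so I take it as two-sided. With pooled variance and no continuity correction,

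n = [1.96 × √(2 p̄(1 − p̄)) + 0.8416 × √(p₁(1 − p₁) + p₂(1 − p₂))]² / (p₁ − p₂)²

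where p̄ = 0.65:

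- 1.96 × √0.455 = 1.322
- 0.8416 × √(0.1875 + 0.2475) = 0.555
- (1.322 + 0.555)² / 0.04 = 88.1, so 89 per arm

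The stated 90 is reproduced, and power at 90 per arm is 80.8%. Other conventions give 86 (unpooled), 88 (arcsine), 98 (continuity-corrected) and 70 (one-sided; 79 with correction). The plan's figure therefore fits a two-sided, uncorrected calculation.

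**2. Does the reversed wording matter?** The formula treats the two rates symmetrically, so swapping the arms gives the same n. Reading the outcome as failure gives 25% against 45%, p̄ = 0.35, the same variances, and again 88.1. That reading does not rescue the sentence, since it would describe a fall from 45% to 25%, but the sample size is unaffected.

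**3. How precise is the target?** The subgroup size is not given, so it must be inferred. Assume that the Background interval is a log-scale Wald interval, that the arms were equal, and that both pairs of rates come from the same women.

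- SE(ln RR) = ln(1.67/1.06)/3.92 = 0.116
- n = (0.09/0.91 + 0.32/0.68)/0.116² = about 42.4 per arm (39.7 to 45.1 when all reported figures vary within rounding)
- Difference for 75% against 55%: SE = √(0.435/42.4) = 0.101, 95% interval 0.1 to 39.9 points (Newcombe, at 42 per arm: −0.4 to 38.2)
- RR = 0.75/0.55 = 1.36, SE(ln RR) = √[(0.25/0.75 + 0.45/0.55)/42.4] = 0.165, 95% interval 0.99 to 1.88
- Pooled z-test p = 0.054, moving between 0.075 and 0.037 as the allocation ratio runs from 0.67 to 1.5

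On these assumptions the 20-point estimate is borderline and wide. For 91% against 68% the corresponding difference interval, at 42 per arm, is about 6 to 40 points.

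**4. Smaller true effects.** Holding the control rate at 55%:

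| True gain | Power at 90 per arm | Per arm for 80% power |
|---|---|---|
| 20 points | 80.8% | 89 |
| 15 points | 54.8% | 163 |
| 10 points | 27.6% | 376 |

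Powering for 15 points would multiply enrolment by 163/90 = 1.8, and for 10 points by 376/90 = 4.2.

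**5. Which contrast was chosen?** Sizing on 91% against 68% would have required 48 per arm, and 90 per arm has 97% power for it. Of the two contrasts in the document, the plan used the more demanding.

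**6. What would a null result show?** At 55% in both arms the 95% half-width is 1.96 × √(2 × 0.2475/90) = 14.5 points. An observed difference of zero would exclude the 20-point target but not a 10-point benefit, and the planned interval would show both facts.

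**The case for a change.** The strongest case for a change is that the target rests on one imprecise estimate from a study with no overall effect, with no clinical argument that 20 points is the right threshold. A trial meant to identify the best induction method could then end with an ambiguous answer: at a true gain of 15 points it is little better than a coin toss. One paragraph giving the source denominators and interval, the power at 10 and 15 points, and the correct direction would cost almost nothing.

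Much of this is true. The target is imprecise, the power figures are right, and the reversed sentence does contradict the one before it. Three limits apply.

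- The range of 0 to 40 points is a reconstruction. It carries one endpoint's interval to another under assumed equal arms and shared women. It supports calling the target imprecise, but it cannot settle whether the subgroup benefit on vaginal delivery was significant.
- The document does not say whether the subgroup was prespecified, so the degree of optimism is unknown. Background openly presents the weakness of the subgroup evidence as the reason for the trial.
- Any fixed sample size has its nominal power only at its assumed rates, and power also depends on the control rate. If that were 68%, the figure Background gives for deliveries, an 18-point gain would already have 82% power at 90 per arm.

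**Conclusion.** No change is called for. The plan states 75% against 55%, 80% power and 90 per arm, and these agree: 89 are needed and 90 give 80.8%, assuming a two-sided test without continuity correction. No figure the plan commits to is missed.

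What remains falls into three parts. The size of the target is a fair trade-off: 20 points is ambitious, but a smaller target means 1.8 to 4.2 times the enrolment, and the trial would still have about twice the inferred subgroup size per arm (90/42.4 = 2.1). The missing interval, denominators and power at smaller effects are gaps in documentation. They do not affect how the data are analyzed, and the planned risk ratio with 95% interval already lets a non-significant result be read for what it does and does not exclude. The reversed sentence is a drafting slip. The preceding sentence and the hypothesis make the intended direction plain, and neither the sample size, the reported estimate nor any conclusion depends on it. The Background citation of reference (4) for the oxytocin study, which the reference list gives as (5), is likewise clerical.

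### The hypothesis claims no added morbidity, but the data list does not commit the trial to record tachysystole, fetal heart rate changes, uterine rupture or prior cesarean

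*Combined protocol and SAP*

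**What the plan says.** The Hypothesis has an efficacy half and a safety half: simultaneous oxytocin "will result in more rapid labor courses, without increase morbidity or increasing the need for operative delivery". Morbidity is not defined.

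Under Study Protocol, both arms receive oxytocin. The experimental arm starts it at balloon placement. The control arm starts it once the balloon has been removed or expelled. Fetal monitoring follows current guidelines in everyone, but it is described as care and not as a study measurement.

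Data Collection answers the operative-delivery part of the hypothesis with "cesarean delivery rate, operative vaginal delivery rate". For the morbidity part it lists "perinatal complications (including postpartum hemorrhage, chorioamnionitis, or cervical laceration), neonatal outcomes (including APGAR scores". The baseline items include parity but not prior cesarean.

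Two other places matter. The Background says of the balloon, in a comparison with prostaglandins, "Foley catheter placement has the advantages of being low cost, with reduced risk of uterine tachysystole or fetal heart rate changes". The Exclusion Criteria remove women with "More than 1 prior cesarean delivery" and those with "Any contraindication to cervical ripening balloon placement or oxytocin administration", so a woman with exactly one prior cesarean can enter if she meets the other criteria.

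**The concern.** The randomized contrast is mainly whether a uterine stimulant runs while the balloon is in place. For that period the plan records time to expulsion and the dilation reached, but it names no measure of how the uterus or fetus responded. The named complications (hemorrhage, chorioamnionitis, cervical laceration) and the Apgar score are not direct measures of uterine activity or of the tracing. Tachysystole that resolves may leave all of them unchanged.

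If these events are left to case-by-case recording, three things can go wrong. Abstraction can differ between charts, because no definition or time window is set. What gets reported can be chosen after the results are seen. And a statement that morbidity did not rise could be made without systematic data on a plausible harm of the intervention. For uterine rupture there is a further gap: without prior-cesarean status at baseline, a reader could not tell how many women with a scar were in each arm.

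**Working it through.** **Step 1. Compare the named items with the safety hypothesis.**

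| Item | Where it appears | Named in Data Collection? |
|---|---|---|
| Cesarean, operative vaginal delivery | Hypothesis (operative delivery) | Yes, but without the indication for cesarean |
| Postpartum hemorrhage, chorioamnionitis, cervical laceration, Apgar | Data Collection | Yes |
| Tachysystole, fetal heart rate changes | Background only | No |
| Uterine rupture | Nowhere | No |
| Prior cesarean (0 or 1) | Exclusion Criteria, as a limit of one | No |

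Both outcome lists are introduced by the word *including*. The gap is therefore one of commitment and definition, not of prohibition.

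**Step 2. Reproduce the planned sample size.** Inputs from Power Calculation: 75% and 55%, 80% power, alpha 0.05. Two-sided testing is assumed, because the plan does not say.

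n = [1.960·√(2·0.65·0.35) + 0.842·√(0.75·0.25 + 0.55·0.45)]² / 0.20² = (1.3221 + 0.5551)² / 0.04 = 88.1, so 89 per arm.

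The plan's 90 agrees. Power at 90 is Φ[(0.20·√90 − 1.3221)/0.6595] = Φ(0.872) = 80.8%. The point here does not depend on this figure, but 90 per arm sets what the safety data can show.

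**Step 3. Expected events and power at assumed rates.** The documents give no tachysystole rate, so these rates are illustrations only.

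Power = Φ[(d·√n − 1.960·√(2·p̄(1−p̄))) / √(p₁(1−p₁) + p₂(1−p₂))], with n = 90.

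- 5% against 10%: expected counts 90·0.05 = 4.5 and 90·0.10 = 9. Power = Φ[(0.4743 − 1.960·0.3725)/0.3708] = Φ(−0.690) = 24.5%.
- 10% against 20%: expected counts 9 and 18. Power = Φ[(0.9487 − 1.960·0.5050)/0.5000] = Φ(−0.082) = 46.7%.

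**Step 4. Width of the interval.** If the observed rates equaled the assumed ones, the 95% confidence interval for the risk difference (unpooled, normal approximation) would be:

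- 5% against 10%: 0.05 ± 1.960·√[(0.0475 + 0.09)/90] = 0.05 ± 0.077, or −2.7 to 12.7 percentage points.
- 10% against 20%: 0.10 ± 1.960·√[(0.09 + 0.16)/90] = 0.10 ± 0.103, or −0.3 to 20.3 percentage points.

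Even an observed doubling could be non-significant.

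**Step 5. Rare events.** With zero events in 90 women, the one-sided 95% upper bound is 1 − 0.05^(1/90) = 3.3%. Within the subgroup with a prior cesarean, whose size the documents do not give, the bound would be wider. Rupture can only be described.

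**The case against.** The case for leaving the plan alone has real strength.

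- *The lists are open-ended.* This stands. A reader might infer that the trial would report none of these events; the documents do not support that, since tachysystole or rupture could be recorded as a perinatal complication. What remains is that no one is bound to do so, and no definition is given.
- *The Background compares the balloon with prostaglandins, which neither arm is assigned.* This also stands. A reader might infer that the protocol itself names tachysystole and heart rate changes as harms of added oxytocin. It does not. Their relevance is an inference, though a reasonable one: the protocol credits the balloon with a low risk of these events and then adds a uterine stimulant to it.
- *Both arms receive oxytocin.* True, so the contrast is mainly one of timing. This is a reason to show the balloon-in-place period separately.
- *Delivery mode and Apgar already reflect fetal intolerance of labor.* Partly. Cesarean is collected without its indication, and a resolved episode need not change either.
- *Transient tachysystole may be a sign and not morbidity.* Fair. Reporting it with and without heart rate changes, beside the clinical outcomes, lets the reader judge.
- *The trial is too small to settle these harms.* Correct, and it limits what the added data can support. It is no reason to leave the events undefined.

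**Conclusion.** The point holds as a gap in prespecification. The plan states a no-added-morbidity hypothesis but does not commit to defining and recording tachysystole, fetal heart rate changes, uterine rupture or prior-cesarean status. The primary outcome and the sample size are unaffected.

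Two further readings go too far. One is that women with a prior cesarean are in the trial in some known number. They are only eligible; no count is given, and the contraindication clauses could exclude some. The other is that adding these items would let the trial establish no increase. At the assumed rates, power is about 25% to 47%, and zero events in 90 still allows a rate up to about 3.3%.

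The size rests on assumed event rates, two-sided testing at 0.05 and 90 analyzed women per arm. That the named lists omit these items rests on the text alone.

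**What to change.** Add to Data Collection, each outcome with a prespecified definition and reported by arm:

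1. uterine tachysystole, with and without fetal heart rate changes, from balloon placement to delivery, with the balloon-in-place period also shown separately;
2. cesarean for non-reassuring fetal heart rate;
3. uterine rupture, descriptive only, with prior cesarean (0 or 1) as a baseline item.

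In the Analysis Plan, state that these will be given as counts with a relative risk or risk difference and its 95% confidence interval, and that a non-significant difference will not be read as no increase in morbidity.

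No extra visit or procedure is needed, since fetal monitoring is already part of care for all participants. The cost is the time to abstract tracings and charts, and a safety result that may look less favorable to the experimental arm.

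### For very rare harms, the relative risk, the only effect measure the plan names, may put no finite upper limit on excess harm; a risk difference with a score-type interval would

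*Combined protocol and SAP*

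**What the plan says.** The Analysis Plan names one effect measure: "Intention to treat analysis, calculation of RR, 95% CI". It does not say which outcomes this covers, how the interval is computed, or what is done when an arm has no events. The only other sentence on method is "Categorical and continuous variables will be assessed using parametric and non-parametric tests where appropriate".

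The Hypothesis has two parts. Simultaneous oxytocin should shorten labor, and it should do so "without increase morbidity or increasing the need for operative delivery". No margin is given for the second part.

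Data Collection lists the outcomes that bear on that part: the cesarean and operative vaginal delivery rates, and "perinatal complications (including postpartum hemorrhage, chorioamnionitis, or cervical laceration), neonatal outcomes (including APGAR scores"). No expected rate is given for any of them.

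The Power Calculation concerns only vaginal delivery within 24 hours, at 75% against 55%, and arrives at 90 women per arm.

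**The concern.** A claim that a treatment does not increase harm is answered by an upper confidence limit on the excess. The RR supplies one only if the control arm has events. With 90 women per arm, a very rare complication may well occur in no control patient, or in nobody at all. The RR is then infinite or undefined.

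The tests sentence leaves room for an exact test, but that yields a p-value and no estimate. At these counts the p-value will almost always be non-significant. The risk is that the report turns this into a statement that morbidity did not increase, with no figure showing how large an increase the data still allow.

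**Working it through.** **1. Inputs.** From the documents: 90 per arm; planning rates 75% and 55%; "Under assumption of 80% power and an alpha of 0.05"; RR as the only named effect measure. Assumed: harm rate p, the same in both arms, from 0.5% to 10%. Differences are experimental minus control.

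**2. The plan's own sample size.** Two-sided test of two proportions, pooled variance under the null, mean rate 0.65:

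n = [1.96 × √(2 × 0.65 × 0.35) + 0.8416 × √(0.75 × 0.25 + 0.55 × 0.45)]² / 0.20² = 88.1, so 89 per arm.

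The stated 90 reproduces; power at 90 per arm is 80.8%. Adding a risk difference to the report does not change this.

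**3. How often an arm is empty.** Let q = (1 − p)^90 be the chance that a given arm has no events. At least one arm is empty with probability 1 − (1 − q)², and both are empty with probability q². The chance that the control arm is empty, whatever happens in the other arm, is q.

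| Assumed rate p | Control arm empty, q | At least one arm empty | Both empty |
|---|---|---|---|
| 0.5% | 64% | 87% | 41% |
| 1% | 40% | 65% | 16% |
| 2% | 16% | 30% | 3% |
| 3% | 6% | 12% | 0.4% |
| 5% | 1% | 2% | 0.01% |
| 10% | 0.01% | 0.02% | about 0 |

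Setting 1 − (1 − q)² = 0.5 gives q = 0.293 and p = 1 − 0.293^(1/90) = 1.35%. Below that rate an empty arm is more likely than not. For the control arm alone, q = 0.5 gives p = 1 − 0.5^(1/90) = 0.77%.

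**4. What the RR delivers with sparse counts.**

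- 2 vs 0: the RR is infinite, and the log-scale interval cannot be computed. A score interval runs from 0.53 to infinity. Adding 0.5 to each cell gives RR = (2.5/91)/(0.5/91) = 5.0, with standard error of log RR √(1/2.5 − 1/91 + 1/0.5 − 1/91) = 1.54 and interval 0.24 to 103.
- 0 vs 0: the RR is undefined.
- 0 vs 2: the RR is 0, and a score interval gives a finite upper limit of 1.89.
- Equal counts in both arms (log-scale interval): 1 vs 1, 0.06 to 15.7; 2 vs 2, 0.14 to 6.9; 5 vs 5, 0.30 to 3.3; 9 vs 9, 0.42 to 2.4. These are estimable but wide.

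**5. What the risk difference delivers.** The Newcombe interval combines the Wilson limits of the two arms. For 0/90 the Wilson upper limit is z²/(n + z²) = 3.84/93.84 = 4.1%.

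| Events, experimental vs control | Risk difference, points | 95% CI |
|---|---|---|
| 0 vs 0 | 0 | -4.1 to +4.1 |
| 1 vs 0 | +1.1 | -3.1 to +6.0 |
| 2 vs 0 | +2.2 | -2.2 to +7.7 |
| 1 vs 1 | 0 | -5.0 to +5.0 |
| 9 vs 9 | 0 | -9.2 to +9.2 |

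Every row has a finite upper limit.

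**6. The primary outcome.** At exactly 75% vs 55% with 90 per arm, the RR is 1.36 (1.09 to 1.70) and the risk difference is 20.0 points (Newcombe 6.1 to 32.9). Both intervals exclude no effect.

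**The case against.** A reader might infer that the listed harms in general are likely to have no usable estimate. The documents do not support that. They give no harm rates, and nothing in them places cesarean delivery, operative vaginal delivery, postpartum hemorrhage or chorioamnionitis below 1.35%. At 5% an empty arm occurs in only 2% of trials. Low Apgar is also not a listed binary outcome: the plan lists scores, which can be analysed as ordinal or continuous.

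Nor is the RR always without a limit when an arm is empty. The plan does not name an interval method, and a score interval gives a finite upper limit when the empty arm is the experimental one. Arm counts would remain, and a reader could derive a difference from them. All of this stands. It narrows the problem to an empty control arm, including 0 vs 0.

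A reader might also infer that the primary analysis is on the wrong scale, because the sizing sentence sets out "to demonstrate a 20% reduction (from 75% to 55%) in primary outcome". That does not follow. The RR is a valid measure of the same comparison, two planning rates fix both scales at once, and reaching 20 points is not a decision criterion anywhere in the plan.

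Finally, a risk difference cannot establish the absence of harm, because no margin is set and 90 per arm is small. That also stands. But an upper limit tells the reader what has not been ruled out, which a p-value does not, and choosing scale and method after seeing the counts is what a plan should prevent.

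**Conclusion.** The point holds in a limited form, for the harm outcomes only. The plan pairs a no-increase hypothesis with an effect measure that, for very rare events, may give no finite upper limit on the excess. An empty control arm, the case that removes the limit, has a chance of 64% at a 0.5% rate, 40% at 1%, 16% at 2% and 1% at 5%. These figures rest on assumed rates, equal in the two arms, and on 90 women analysed per arm. Which listed harms are that rare cannot be told from the documents.

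For more common harms the RR is estimable and the issue is imprecision, which changing the scale does not cure. The primary analysis and the sample size are unaffected. The change is worth making before analysis because the no-increase claim depends on how these outcomes are reported.

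**What to change.** Add to the Analysis Plan: *For each binary harm outcome (cesarean delivery, operative vaginal delivery, postpartum hemorrhage, chorioamnionitis, cervical laceration), the number of events and of women in each arm will be reported, with the risk difference and a score-type 95% CI (Newcombe or Miettinen-Nurminen). The RR and its 95% CI will be given beside it where estimable. Conclusions about morbidity will be worded by the upper limit of the risk-difference interval, not by the absence of statistical significance.*

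Add that, with no margin set, 90 per arm can bound an excess of harm but cannot establish its absence. Reporting the risk difference for the primary outcome as well is optional good practice.

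The cost is a short addition to the plan, one more column in the results tables and a more cautious morbidity statement. It needs no new data and no change in sample size.
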